9.4.3. Secondary Endpoints

All secondary endpoints will be summarized with descriptive statistics by treatment arm and overall among all participants in an appropriate analysis set. Categorical variables will be summarized with the number and percent of participants in each category. Continuously variables will be summarized with N, mean, standard deviation, 95% 2-sided confidence interval, median, first quartile (Q1), third quartile (Q3), minimum, and maximum.

In addition, the difference in the percentage of MG-ADL responders between the 2 treatment arms will be analyzed using the meta-analysis predictive approach while incorporating the treatment cycle 1 data from the efgartigimod IV treatment arm in study ARGX-113-1704 as historical active controls.⁷

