4.2. Scientific Rationale for Study Design

The aim of this study is to assess the PD, PK, safety, tolerability, immunogenicity, and clinical efficacy of efgartigimod coadministered with rHuPH20 subcutaneously (efgartigimod PH20 SC) as compared to efgartigimod IV in patients with gMG. IgG autoantibodies lead to gMG

Clinical Study Protocol ARGX-113-2001 v2.0 Efgartigimod IV and SC

symptoms, resulting from destruction of important molecules in the NMJ, including AChR. IgG antibody total levels, levels of IgG subtypes (IgG1, IgG2, IgG3, and IgG4), and levels of AChR-Abs will be evaluated as an objective surrogate measure for gMG treatment efficacy, as study ARGX-113-1704 showed that reduction total IgG levels and AChR-Ab levels (in AChR-Ab seropositive participants) correlate with reductions in the MG-ADL total score. Clinical efficacy will be measured by the MG-ADL total score and the QMG score, which are well-established measures for assessing disease severity.

The PD of efgartigimod IV at 10 mg/kg and efgartigimod PH20 SC at a fixed dose of 1000 mg will be compared, as per the primary objective of this study (see Section 3). The SC formulation of efgartigimod will include rHuPH20 because the enzyme facilitates the SC delivery of volumes greater than \sim 2 mL and may increase the absorption and dispersion of efgartigimod. rHuPH20 has been approved in the United States as Hylenex recombinant as a permeation enhancer for SC delivery of fluid for achieving hydration and as an adjuvant to increase the dispersion and absorption of other injected drugs. rHuPH20 depolymerizes hyaluronan under physiologic conditions, allowing for a larger volume to be used in rapid SC injections with limited swelling, induration or pain.^{5,6}

The open-label design used in this study will have no impact on the assessment of the PD, PK, and immunogenicity parameters and thus is not expected to impact the primary endpoint and most of the secondary endpoints. Importantly, a double blind study design would be more burdensome for the participants.

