8.1.2.1. MG-ADL

The MG-ADL is an 8-item patient-reported scale that assesses MG symptoms and their effects on daily activities. It evaluates a participant's capacity to perform different activities in their daily life, including talking, chewing, swallowing, breathing, brushing their teeth, combing their hair, or getting up from a chair. The MG-ADL also assesses double vision and eyelid droop. It is a discrete quantitative variable in which the 8 items are rated by the participant on a scale of 0 to

Clinical Study Protocol ARGX-113-2001 v2.0 Efgartigimod IV and SC

3. The total score can range from 0 to 24, with higher total scores indicating more impairment. The MG-ADL assessment does not require any equipment to perform. The scoring of the MG-ADL should be performed by a trained and certified evaluator.

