9. STATISTICAL CONSIDERATIONS

The statistical analysis will be performed by the sponsor's designated CRO using statistical analysis systems (SAS) software (SAS Institute, Cary, NC, United States) version 9.4 or higher, and the software package R, if applicable. The standard operating procedures (SOPs) and work instructions of the sponsor's designated CRO will be used as the default methodology if not otherwise specified.

A detailed and comprehensive Statistical Analysis Plan (SAP) will be written and signed-off prior to final analysis database lock. Minor changes to the statistical methods set out in this protocol do not require a protocol amendment but will be documented (as changes from the protocol) in the SAP and in the clinical study report(s). The below sections contain the main general features of the statistical analysis. More details will be provided in the SAP.

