Seventy-six participants would suffice for the noninferiority comparison between SC and IV based on IgG reduction at day 29; however, increasing the sample size to approximately 110 participants will provide better quantification of the clinical safety and efficacy profile of the SC formulation in patients with gMG while the IV formulation will serve as a reference treatment in this randomized study.

Note: "Enrolled" means a participant's, or their legally acceptable representative's, agreement to participate in a clinical study following completion of the informed consent process and screening. Potential participants who are screened to determine eligibility for the study, but do not participate in the study, are not considered enrolled unless otherwise specified by the protocol. "Randomized" means that an enrolled participant has been randomly assigned to a treatment arm.

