9.4. Statistical Analyses

The SAP will be finalized before database lock and will include a more technical and detailed description of the statistical analyses described in this section. This section is a summary of the

planned statistical analyses of the most important endpoints including primary and key secondary endpoints.

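### Does Section 9.4.3 let a historical IV arm displace the randomized SC-IV comparison of MG-ADL responders?

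*Protocol*

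**What the plan says.** Section 9.4.3 opens with descriptive statistics by treatment arm and overall for every secondary endpoint. For responder endpoints this means: "Categorical variables will be summarized with the number and percent of participants in each category". It then continues: "In addition, the difference in the percentage of MG-ADL responders between the 2 treatment arms will be analyzed", using a "meta-analysis predictive approach while incorporating the treatment cycle 1 data from the efgartigimod IV treatment arm in study ARGX-113-1704 as historical active controls". It states no prior, no decision rule and no ranking of the two presentations.

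Section 9.4 calls itself a summary covering the "planned statistical analyses of the most important endpoints including primary and key secondary endpoints" and leaves the technical description to the SAP. Section 9 also refers to the SAP for detail and adds: "Minor changes to the statistical methods set out in this protocol do not require a protocol amendment".

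Section 9.2 says 76 participants are enough for the noninferiority test. It raises the number to about 110 to describe the clinical safety and efficacy of SC better, "while the IV formulation will serve as a reference treatment in this randomized study". In Section 3, the pharmacodynamic secondary objective is to compare the two formulations over time; the clinical efficacy objective is to evaluate each.

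**The concern.** Three features make the choice look wrong.

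- The only between-arm clinical contrast in the section is a borrowed one. Confidence intervals are listed for continuous variables but not for categorical ones, so no interval for a randomized-only responder difference is announced.
- There is one historical study. One study carries no information on between-study variance, so the assumed prior decides how much history counts.
- The settings differ. ARGX-113-1704 was placebo-controlled; this trial is open-label with active drug in both arms. Section 8.1.2.1 states: "The MG-ADL is an 8-item patient-reported scale that assesses MG symptoms". Section 4.2 argues that the open-label design does not affect PD, PK and immunogenicity, and "thus is not expected to impact the primary endpoint and most of the secondary endpoints"; it does not name MG-ADL.

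If the IV responder rate differed between the studies, the SC-IV difference would be pulled toward or away from SC. The sample was enlarged to describe clinical efficacy against a randomized reference, so that would matter for how SC efficacy is read.

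**Working it through.** **1. What the text fixes.** Section 9.4.3 gives two layers: counts and percentages by randomized arm, then, as an addition, the borrowed difference. Nothing calls the second the main estimate or replaces the first. Two counts with their denominators give the concurrent difference and its interval directly.

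**2. The plan's own figures.** The protocol attaches no sample size or precision to MG-ADL responders. Its figures concern the primary test (margin 10, true difference 2, 1-sided 2.5%, 90% power). The t-test calculation reproduces them: 20, 25 and 34 per arm for SD 7.5, 8.5 and 10 (power 0.908, 0.903, 0.902), that is 40, 50 and 68 in total. Borrowing does not enter that test.

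**3. Inputs for the size check.**
- Historical IV responder rate 67.9%, overall population (Section 2.3.2).
- Historical N is not stated. From SD 7.5 and SE 0.82 (Section 9.2): (7.5/0.82)² = 83.7, taken as 84. 57/84 = 67.9% agrees.
- 55 per arm (110 randomized 1:1, before attrition).
- Assumed: half-normal prior on the between-study SD (logit scale) with scale 1.0, 0.5, 0.25 or 0.1. True SC-IV difference 0.

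**4. Weight of history.** Historical logit = ln(57/27) = 0.747; SE = √(1/57 + 1/27) = 0.234. With mean m and variance v of the predictive prior for the rate, the effective sample size is m(1−m)/v − 1: about 4, 10, 27 and 62 participants for the four scales. The posterior median of the between-study SD essentially equals its prior median (0.066, 0.166 and 0.336 for scales 0.1, 0.25 and 0.5; 0.667 against 0.672 for scale 1.0). The prior does set the weight.

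**5. Precision at 67.9%.** Concurrent only: 1.96 × √(2 × 0.679 × 0.321/55) = 17.4 points per side. Borrowed: 16.4, 16.0, 15.5 and 14.9.

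**6. Bias, coverage and error.** The interval is (SC proportion − posterior mean of the IV rate) ± 1.96 × √(posterior variance of the IV rate + SC p(1−p)/55), evaluated exactly over the binomial counts. Values run from scale 1.0 to scale 0.1; the 5-point row gives the range over priors and both directions.

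| True rate, both arms | Shift in SC-IV (points) | Coverage (%) | RMSE, borrowed | RMSE, concurrent only |
|---|---|---|---|---|
| 78% | +1.9 to +5.6 | 93.9, 93.1, 92.0, 86.7 | 7.7, 7.7, 7.9, 8.3 | 7.9 |
| 72.9% or 62.9% | +1.1 to +2.9, or −1.0 to −2.5 | 94.0 to 95.7 | 7.2 to 8.4 | 8.5 or 9.2 |
| 67.9% | about 0.1 | 95.8 to 96.4 | 8.0, 7.7, 7.3, 6.9 | 8.9 |
| 58% | −1.8 to −5.1 | 94.8, 94.6, 93.7, 91.6 | 9.0, 8.9, 8.8, 9.0 | 9.4 |

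At 78% and 58%, concurrent-only coverage is about 94.5%.

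**7. Reading the table.** Borrowing loses on RMSE in one cell only: scale 0.1 with a true rate of 78%. Coverage is below 92% only with scale 0.1 and a drift of about 10 points. That pairing is extreme on the prior's own terms. A rate of 78% lies ln(0.78/0.22) − 0.747 = 0.52 logits from history. The predictive SD under scale 0.1 is about √(0.234² + 2 × 0.1²) = 0.273, so the drift is about 1.9 predictive SDs.

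**The case for a change.** The best argument for the concern is about prespecification. In an open-label trial with two possible responder contrasts, leaving their order open lets someone choose the lead after seeing both. One historical study makes the borrowed result depend on its prior, and naming the randomized difference first would cost one sentence and 1 to 2.5 points of interval half-width per side.

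The facts in this stand: the prior decides the weight, the settings differ, and the protocol announces no interval for the concurrent difference. They do not amount to an error, for four reasons.

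- With no success rule, no decision depends on which contrast is printed first.
- The randomized counts are committed to in the same section, so the concurrent result cannot be withheld.
- Sections 9 and 9.4 leave such detail to the SAP. It was not available and may already contain the concurrent estimate, so its absence from the protocol shows nothing.
- Borrowing adds to the randomized IV arm rather than replacing it, so it does not conflict with the purpose given in Section 9.2.

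The protocol also gives grounds for borrowing: the two studies share the IV regimen and the MG-ADL entry rule, and both admit AChR-Ab negative patients. Open-label reporting bias within this trial would affect a concurrent-only estimate as well, so it does not favour one analysis over the other.

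**Conclusion.** The concern does not hold. Section 9.4.3 reports the randomized responder results by arm and supplements them with a borrowed difference; it neither contradicts another section nor produces a wrong result if followed as written. What remains is a trade of bias against precision in a secondary analysis without a decision attached. On the assumptions used, that trade favours borrowing, or is about neutral, in every scenario but one (RMSE 8.3 against 7.9 points). At equal rates the shift is about 0.1 point.

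The figures rest on an inferred historical N of 84, full retention of 55 per arm, illustrative priors and assumed drifts; the protocol states no prior and predicts no drift. With historical N between 60 and 110 and the tightest prior, borrowing is worth 48 to 75 participants and the shift at a true rate of 78% is 5.0 to 6.0 points. These figures do not alter the reading of the text, on which the conclusion mainly rests. The primary IgG conclusion is unaffected throughout.

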9.4.4. Exploratory Endpoints

Exploratory endpoints will be summarized with descriptive statistics by treatment arm and overall among all participants in the ITT analysis set.

9.5. Interim Analysis

Interim analyses may be performed to support questions from authorities and/or submissions.

10. SUPPORTING DOCUMENTATION AND OPERATIONAL CONSIDERATIONS

10.1. Appendix 1: Regulatory, Ethical, and Study Oversight Considerations

10.1.1. Regulatory and Ethical Considerations

This study will be conducted in accordance with the protocol and with the following:

- Consensus ethical principles derived from international guidelines including the Declaration of Helsinki and Council for International Organizations of Medical Sciences (CIOMS) International Ethical Guidelines
- Applicable International Council for Harmonisation (ICH) Good Clinical Practice (GCP) Guidelines
- Applicable laws and regulations

The protocol, protocol amendments, ICF, IB, and other relevant documents (eg, advertisements) must be submitted to an Institutional Review Board/Independent Ethics Committee (IRB/IEC) by the investigator and reviewed and approved by the IRB/IEC before the study is initiated.

- Any amendments to the protocol will require IRB/IEC approval before implementation of changes made to the study design, except for changes necessary to eliminate an immediate hazard to study participants.
- Protocols and any substantial amendments to the protocol will require health authority approval prior to initiation except for changes necessary to eliminate an immediate hazard to study participants.

The investigator will be responsible for the following:

- Providing written summaries of the status of the study to the IRB/IEC annually or more frequently in accordance with the requirements, policies, and procedures established by the IRB/IEC
- Notifying the IRB/IEC of SAEs or other significant safety findings as required by IRB/IEC procedures
- Providing oversight of the conduct of the study at the site and adherence to requirements of 21 Code of Federal Regulations (CFR), ICH guidelines, the IRB/IEC, European regulation 536/2014 for clinical studies, and all other applicable local regulations

10.1.2. Financial Disclosure

The sponsor will fund the study as outlined in the clinical study agreement.

The sponsor will obtain adequate global/local insurance for the study participants including the study participants for the required duration of time.

Clinical Study Protocol ARGX-113-2001 v2.0 Efgartigimod IV and SC

The sponsor maintains an insurance coverage for this study in accordance with the laws and regulations of the countries in which the study is performed. Liability and insurance provisions for this study are specified in the investigator's contract. The terms and conditions will apply as specified in the policy document.

Investigators and sub-investigators will provide the sponsor with sufficient accurate financial information as requested to allow the sponsor to submit complete and accurate financial certification or disclosure statements to the appropriate regulatory authorities. Investigator are responsible for providing information on financial interests during the course of the study and for 1 year after completion of the study.

10.1.3. Informed Consent Process

- Prior to signing the ICF, the study participants will be instructed not to participate in any other clinical study that involves a therapeutic intervention until the completion of the study.
- Any participant that provides informed consent will be assigned a unique participant ID via the Interactive Response Technology (IRT) system.
- The investigator or his/her representative will explain to the participant all of the following: the nature of the study, its purpose, the procedures involved, the expected duration, any potential discomfort, potential alternative procedure(s) or course(s) of treatment available, and the extent of maintain the confidentiality of the participant's records. The investigator or his/her representative will answer all questions from the participant regarding the study.
- Participants must be informed that their participation is voluntary, that they may withdraw from the study at any time, and that withdrawal of consent will not affect their subsequent medical treatment or relationship with the treating physician.
- Participants will be required to sign a statement of informed consent, after receipt of detailed information on the study, that meets the requirements of 21 CFR 50, local regulations, ICH guidelines, Health Insurance Portability and Accountability Act (HIPAA) requirements, where applicable, and the IRB/IEC or study center.
- The ICF will be used to explain the potential risks and benefits of study participation to the participant in simple terms before the participant is screened.
- The medical record must include a statement that written informed consent was obtained before the participant was enrolled in the study and the date the written consent was obtained. The authorized person obtaining the informed consent must also sign the ICF.
- A separate ICF will be issued in case of pregnancy of a female partner of a male participant. If required by local regulations, a separate pregnancy ICF will be issued for female participants who become pregnant.
- All participant information and ICFs must be available in the local and vernacular languages required at the site and include participant information sheets/brochures

Clinical Study Protocol ARGX-113-2001 v2.0 Efgartigimod IV and SC

that outline the study procedures. All ICF(s) must be signed and dated by the participant.

- Participants must reconsent to the most current version of the ICF(s) during their participation in the study.
- The investigator is responsible for ensuring that informed consent is obtained from each participant and for obtaining the appropriate signatures and dates on the ICF prior to the performance of any protocol procedures and prior to the administration of the IMP.
- A copy of the signed and dated ICF(s) must be provided to the participant.
- A participant who is rescreened or retested is not required to sign another ICF if the rescreening occurs within the screening period.

10.1.4. Data Protection

- Participants will be assigned a unique identifier by the sponsor. Any participant records or datasets that are transferred to the sponsor will contain the identifier only; participant names or any information which would make the participant identifiable will not be transferred.
- The participant must be informed that his/her personal study-related data will be used by the sponsor in accordance with local data protection law. The level of disclosure must also be explained to the participant who will be required to give consent for their data to be used as described in the informed consent.
- The participant must be informed that his/her medical records may be examined by Clinical Quality Assurance auditors or other authorized personnel appointed by the sponsor, by appropriate IRB/IEC members, and by inspectors from regulatory authorities.

10.1.5. Committees Structure

10.1.5.1. Data Safety Monitoring Board

- Participant safety will be monitored by an independent DSMB, which includes safety signal detection at any time during the study.
- The DSMB will consist of an independent group of clinical experts who are not involved in the study management. The objective of the DSMB will be to review and evaluate all available safety data. The planning and frequency of the meetings will be detailed in the DSMB charter. Additionally, ad hoc meetings can be requested at any time during the study by the sponsor or the DSMB.
- The DSMB will advise the sponsor regarding continuation, modification, temporary discontinuation, or termination of the study after every meeting.
- The composition, objectives, role, and responsibilities of the DSMB will be described in the DSMB charter, which will be agreed to by the DSMB members and the

sponsor. The DSMB charter will also define and document the content of safety summaries and general procedures, including communications.

10.1.6. Dissemination of Clinical Study Data

- The sponsor or designee and auditor may access participant records for the purpose of monitoring this study, auditing, and managing progress details. The investigator must be fully aware that the sponsor or designee and auditor can inspect or verify documents to verify participant's chart and eCRF records. Such information must be kept confidential in locked facilities that allow for this. The investigator will prepare and maintain adequate and accurate source documents to record all observations and other pertinent data for each participant screened for the study.
- The investigator is responsible for maintaining source documents. These will be made available for verification by the sponsor's designated CRO monitor at each monitoring visit. The investigator must submit an eCRF for each participant, regardless of duration of participation or administration of IMP (ie, an eCRF has to be submitted for screen failures as well). All supportive documentation submitted with the eCRF, such as laboratory or hospital records, should be clearly identified with the study and participant number. Any personal information, including participant name, should be removed or rendered illegible to preserve data privacy.

10.1.7. Data Quality Assurance

- All participant data relating to the study will be recorded on printed or electronic CRF unless transmitted to the sponsor or designee electronically (eg, laboratory data). The investigator is responsible for verifying that data entries are accurate and correct by electronically signing the CRF.
- The investigator must maintain accurate documentation (source data) that supports the information entered in the eCRF if and where applicable. No source data verification will be performed on race and ethnicity only if requested per local regulations.
- Guidance on completion of eCRFs will be provided in the eCRF completion guidelines by the designated CRO.
- The investigator must permit study-related monitoring, audits, IRB/IEC review, and regulatory agency inspections and provide direct access to source data documents.
- Monitoring details describing strategy (eg, risk-based initiatives in operations and quality such as Risk Management and Mitigation Strategies and Analytical Risk-Based Monitoring), methods, responsibilities and requirements, including handling of noncompliance issues and monitoring techniques (central, remote, or on-site monitoring) are provided in the monitoring plan.
- The sponsor or designee is responsible for the data management of this study, including quality checking of the data.
- The sponsor assumes accountability for actions delegated to other individuals (eg, CROs).

Clinical Study Protocol ARGX-113-2001 v2.0 Efgartigimod IV and SC

• Study monitors will perform ongoing source data verification to confirm that data entered into the eCRF by authorized site personnel are accurate, complete, and verifiable from source documents; that the safety and rights of participants are being protected; and that the study is being conducted in accordance with the currently approved protocol and any other study agreements, ICH GCP, and all applicable regulatory requirements.

